## Appendix III:

### Neurocognitive Function Assessments Background Information and Test Instructions

There are three immediate recall responses, one delayed recall response, and one delayed recognition response in the HVLTR. The response is the number of words the patient can recall out of 12 words for recall responses and the difference of the listed words correctly and incorrectly recalled for recognition response. The response from Trail Making Test, parts A & B is the time takes to finish each test less than 3 and 5 minutes, respectively. There are three responses for the COWAT, and each response is the number of words starting with a provided letter of the alphabet that the patient can produce in one minute.

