#### 11.2.2.2 Trail Making Test (TMT)

This is a measure of visuospatial scanning, attention, sequencing, and speed Part A and executive function in Part B. Patients must “connect the dots” either in a numbered sequence or alternating letters and numbers. Generally Part A and Part B require less than 5 minutes, and Part A is discontinued at 3 minutes, Part B at 5 minutes, to reduce burden on patients with significant cognitive impairment.

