#### 13.3.2 Secondary Endpoints

##### 13.3.2.1 Cognitive Function and Fatigue

All the secondary cognitive and fatigue endpoints will be analyzed similar to the primary endpoint. Additionally, the relationship between the change from baseline through 12 months in cognitive and fatigue endpoints will be evaluated using Spearman correlation coefficients.

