#### Testing: General Information

1. Testing should be completed in one session. Test instructions must be followed verbatim with every patient at every assessment visit.
2. Tests should be administered in the following order to every patient and at each assessment visit: HVLTR Part A (Learning Trials); Trail Making Test Part A; Trail Making Test Part B; COWAT; HVLTR Part B (Delayed Recall); and the HVLTR Part C (Delayed Recognition).
3. Follow the instructions on the Forms Packet Index before submitting the forms.
4. All test results are recorded on the Neurocognitive Evaluation Summary Form (CS), which is found in the Forms Packet. Study/case-specific labels must be applied to all forms.
5. **Note:** Sites should keep all original test records, and test results must remain on file at the institution as source documentation pending request for submission by a Study Chair.
6. Patients should not be given copies of their tests to avoid learning the material between test administrations.
7. The HVLTR and the COWAT have alternate forms or versions in order to reduce the effects of practice. See the test instructions below for the versions to be administered at pre-treatment and subsequent sessions. The forms should continue to be alternated in this order for the duration of the study. The forms packet will contain alternate versions of these neuropsychological tests.

Before dismissing the patient, thank him/her for their cooperation. Remind the patient of their next appointment and that these tests will be repeated.

In the event that a patient cannot complete a given test, please write the reason(s) on the test form AND the data summary form.

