**Examiner:** *“Good! Let’s try the next one. On this page are numbers from 1 to 25. Do this the same way. Begin at number 1 (point) and draw a line from 1 to 2 (point to 2), 2 to 3 (point to 3), 3 to 4 (point to 4) and so on, in order, until you reach the circle marked END (point). Do not skip around, but go from one number to the next in proper order. Remember to work as fast as you can. Ready, begin.”*

- Start timing as soon as the instruction is given to “begin”
- Watch closely in order to catch any errors as soon as they are made. If the patient makes an error, call it to his/her attention immediately and have him/her proceed from the point the mistake occurred
- The patient must complete the test in **3 minutes** or less.
- **DO NOT STOP TIMING UNTIL HE/SHE REACHES THE CIRCLE MARKED “END”.**
- Collect the worksheet and record the time to completion on the Trail Making Data Sheet in minutes and seconds
- If the patient does not complete the test within **3 minutes** terminate the testing. The test can also be discontinued if the patient is extremely confused and is unable to perform the task. Collect the worksheet and complete the Trail Making Data Sheet indicating the reason the test was terminated and the last correct number reached on the test.

**Part B – Sample:** Place the Sample B worksheet flat on the table, directly in front of the patient (the bottom of the worksheet should be approximately six inches from the edge of the table) and say:

**Examiner:** *“On this page (point) are some numbers and letters. Begin at number 1 (point to 1) and draw a line from 1 to A (point), A to 2 (point to 2), 2 to B (point to B), B to 3 (point to 3), 3 to C (point to C) and so on, in order, until you reach the end (point to the circle marked END). Remember, first you have a number (point to 1), then a letter (point to A), then a number (point to 2), then a letter (point to B), and so on. Draw the lines as fast as you can. Ready, begin.”*

If the patient completes Sample B correctly, and in a manner demonstrating that s/he understands what to do, proceed immediately to Part B. If the patient makes a mistake on Sample B, point out the error and explain it.

The following explanations of mistakes serve as illustrations:

- *You started with the wrong circle. This is where you start (point to number 1)*
- *You skipped this circle (point to the circle omitted)*

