### **Part B – Test:**

After the patient has completed Sample B, place the Part B Worksheet directly in front of the patient and say:

**Examiner:** *“Good! Let’s try the next one. On this page are both numbers and letters. Do this the same way. Begin at number 1 (point) and draw a line from 1 to A (point to A), A to 2 (point to 2), 2 to B (point to B), B to 3 (point to 3), 3 to C (point to C) and so on, in order, until you reach the circle marked END (point). Remember, first you have a number (point to 1), then a letter (point to A), then a number (point to 2), then a letter (point to B), and so on. Do not skip around, but go from one circle to the next in the proper order. Draw the lines as fast as you can. Ready, begin.”*

- Start timing as soon as the instruction is given to “begin”.
- Watch closely in order to catch any errors as soon as they are made. If the patient makes an error, call it to his/her attention immediately and have him/her proceed from the point the mistake occurred
- The patient must complete the test in **5 minutes** or less.
- **DO NOT STOP TIMING UNTIL HE/SHE REACHES THE CIRCLE MARKED “END”.**
- Collect the worksheet and record the time to completion on the Trail Making Data Sheet in minutes and seconds.
- If the patient does not complete the test within 5 minutes terminate the testing. The test can also be discontinued if the patient is extremely confused and is unable to perform the task. Collect the worksheet and complete the Trail Making Data Sheet indicating the reason the test was terminated and the last correct number or letter reached on the test.

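### Trail Making is scored only for patients who finish, so a patient who finishes at baseline and times out later has no change score, which biases mean decline toward no harm.

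*Combined protocol and SAP*

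**What the plan says.** Trail Making Parts A and B are secondary endpoints (section 13.1.2.1) and belong to the battery for time to neurocognitive failure (objective 2.2.1).

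- **Score.** In the background text of Appendix III, the response from each part "is the time takes to finish each test less than 3 and 5 minutes, respectively".
- **Limits.** Section 11.2.2.2: "Part A is discontinued at 3 minutes, Part B at 5 minutes, to reduce burden on patients with significant cognitive impairment".
- **Part A not finished.** The Appendix III instructions tell the examiner to "complete the Trail Making Data Sheet indicating the reason the test was terminated and the last correct number reached on the test". They add: "The test can also be discontinued if the patient is extremely confused and is unable to perform the task".
- **Part B not finished.** "If the patient does not complete the test within 5 minutes terminate the testing". The data sheet is then completed "indicating the reason the test was terminated and the last correct number or letter reached on the test".
- **Any test not completed.** "In the event that a patient cannot complete a given test, please write the reason(s) on the test form AND the data summary form".
- **Analysis.** Section 13.3.2.1: "All the secondary cognitive and fatigue endpoints will be analyzed similar to the primary endpoint". For the primary endpoint, section 13.2 defines each patient's change as (baseline − 3 months) / baseline, and section 13.3.1 tests the mean with a one-sided one-sample t-test at 0.05.

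No section turns a time-out into an analysis value. There is no cap, no worst rank, no failure category and no missing-data rule.

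**The concern.** The score exists only for patients who finish, and the change score needs two finishing times. Someone whose Part B time goes from 150 s to 170 s counts as a mild worsening. Someone who goes from 250 s to not finishing counts as nothing. By the rationale in section 11.2.2.2, the time limits bear mainly on the most impaired patients, so the lost values are not a random subset. These patients came to the visit and were tested; this is separate from death or a missed visit.

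In a single-arm trial no comparison group would share the distortion. The estimate of mean Trail Making decline moves toward no harm. If the handling is left to the analyst, the choice is made after the data have been seen.

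**Working it through.** The plan states no Trail Making effect, standard deviation or time-out rate, so there is no figure of its own to reproduce. The check has two parts: what the rules imply for one patient, and how large the effect could be on assumed inputs.

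**1. One patient (limits from section 11.2.2.2, formula from section 13.2)**

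- Part B 150 s, then 170 s: (150 − 170)/150 = −0.13. It can be computed, but worsening has a negative sign because a longer time is worse. Section 13.3.2.1 sets neither a direction nor a null value for Trail Making.
- Part B 250 s, then not finished at 300 s: no follow-up time is defined, so no change score exists.

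From here on, worsening is (follow-up − baseline)/baseline, so that slowing is positive.

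**2. Simulation on assumed inputs**

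Part B baseline is log-normal with log-SD 0.5. The median slowing is 30% and the log-SD of change is 0.35. Patients finish at baseline (under 300 s). The true mean worsening is 1.30 × exp(0.35²/2) − 1 = 1.30 × 1.063 − 1 = 38%.

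| Median baseline | Time out at follow-up | True | Finishers only | Time-outs set to 300 s |
|---|---|---|---|---|
| 100 s | 7% | 38% | 33% | 35% |
| 130 s | 14% | 38% | 29% | 32% |
| 160 s | 20% | 38% | 26% | 29% |

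The bias is about 5, 9 and 13 percentage points.

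**3. Less slowing, same model and the same three medians**

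- Median slowing 10% (true mean 17.0%): 4% to 12% time out. Finishers show 14.1%, 11.8% and 9.4%, a bias of 2.9, 5.2 and 7.6 points.
- No median slowing (true mean 6.3%): 3% to 9% time out. Finishers show 4.4%, 2.6% and 0.9%, a bias of 1.9, 3.7 and 5.4 points.

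**4. Different assumptions**

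With medians of 90, 120 and 150 s, log-SD 0.4 for both baseline and change, and a true worsening of 20%, 50% or 100%, dropping time-outs understated decline in all nine combinations. It was always further from the truth than capping. For a true 50%, dropping gives 43%, 37% and 31%; capping gives 47%, 42% and 37%.

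**5. Small numbers**

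Take 18 patients, the analysable number that section 13.2 gives for the primary endpoint, with finishers slowing 20% on average. Assume that those who time out had a baseline of 120 s, so the cap scores them (300 − 120)/120 = 150%.

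- Two time-outs: (16 × 20% + 2 × 150%)/18 = 34%.
- Four time-outs: (14 × 20% + 4 × 150%)/18 = 49%.
- Time-outs dropped: 20%, however many there are.

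**6. Patients who already time out at baseline**

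In the model of step 2, 1.4%, 4.7% and 10.4% of patients exceed 300 s at baseline. Capped there, they can show only no change or improvement. Capping everyone gives mean worsening of 34%, 30% and 26%, against 33%, 29% and 26% for finishers only. Most of the recovery is lost, and at 160 s practically all of it. A cap therefore has to be limited to baseline finishers.

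**The case against.** A reader might infer that the protocol directs patients who time out to be removed. It does not. Exclusion is what follows from a score defined for finishers, a change score that needs two values, and no substitution rule. The defining sentence is loosely worded background text, the elapsed time at a time-out is known to be the limit, and a coding rule may sit on the data sheet or summary form in the Forms Packet, which the documents do not reproduce. That stands, so the claim is about the plan as written.

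A reader might also infer that executive function goes without a sound measure. Section 11.2.2.2 assigns it to Part B, but section 11.2.2.3 says that COWAT also assesses executive skills, and COWAT is a word count with no finishing requirement.

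Nor do the documents support a claim that objective 2.2.1 is undone by time-outs in particular. It gives no failure threshold for any test, and section 13.3 has no time-to-failure analysis. That gap is wider than this point.

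The size is open to challenge. Every input is assumed, section 11.2.2.2 says the parts generally take less than 5 minutes, and eligibility requires a Karnofsky status of at least 70. With 18 patients the standard error of the mean is roughly 8 to 11 points, so the bias is often one standard error or less. This limits how much the bias would matter in practice. It does not change the direction, and the bias does not shrink as patients are added.

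**Conclusion.** The point holds in a limited form. Applied as written, the plan gives no change score to a patient who finishes Trail Making at baseline and times out or is too confused at follow-up, and this understates mean decline. The direction rests on one step that the documents leave implicit: that a test without a finishing time is not otherwise scored.

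The size cannot be known from the documents. On the assumed inputs it runs from about 2 points with little slowing to about 13 points with 30% median slowing and a median baseline of 160 s.

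Only a secondary endpoint is affected. The primary endpoint is a count of words out of 12 and has no time limit of this kind, and neither the sample size nor the primary test changes. The matter should be settled before analysis, but it does not threaten the trial's main conclusion.

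**What to change.** - **Appendix III.** For a patient who finished at baseline, score a follow-up time-out or a stop for confusion at the limit (180 s for Part A, 300 s for Part B), flagged as censored.
- **Section 13.3.2.1.** Analyse Trail Making change with a rank-based paired test (sign or signed-rank) in which finisher to non-finisher is the worst change. State that a longer time is worsening, since the formula in section 13.2 gives it a negative sign.
- **Baseline non-finishers.** Report them separately, because they cannot worsen against the cap.
- **Reporting.** Give the number of time-outs and other stops, with reasons, at each visit.
- **Objective 2.2.1.** If Trail Making is used for time to neurocognitive failure, count finisher to non-finisher as a decline.

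The cost is one scoring rule and a few sentences. The reason and the last circle reached are already recorded, so no new data are needed and the rule can be applied to patients already enrolled. The downside is that reported Trail Making decline becomes somewhat larger. A capped mean still understates it (35%, 32% and 29% against 38% in the illustration), which is why the test should rest on ranks and not on the capped mean.

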#### Testing: General Information

1. Testing should be completed in one session. Test instructions must be followed verbatim with every patient at every assessment visit.
2. Tests should be administered in the following order to every patient and at each assessment visit: HVLTR Part A (Learning Trials); Trail Making Test Part A; Trail Making Test Part B; COWAT; HVLTR Part B (Delayed Recall); and the HVLTR Part C (Delayed Recognition).
3. Follow the instructions on the Forms Packet Index before submitting the forms.
4. All test results are recorded on the Neurocognitive Evaluation Summary Form (CS), which is found in the Forms Packet. Study/case-specific labels must be applied to all forms.
5. **Note:** Sites should keep all original test records, and test results must remain on file at the institution as source documentation pending request for submission by a Study Chair.
6. Patients should not be given copies of their tests to avoid learning the material between test administrations.
7. The HVLTR and the COWAT have alternate forms or versions in order to reduce the effects of practice. See the test instructions below for the versions to be administered at pre-treatment and subsequent sessions. The forms should continue to be alternated in this order for the duration of the study. The forms packet will contain alternate versions of these neuropsychological tests.

Before dismissing the patient, thank him/her for their cooperation. Remind the patient of their next appointment and that these tests will be repeated.

In the event that a patient cannot complete a given test, please write the reason(s) on the test form AND the data summary form.

#### Testing: Specific Instructions

**Note:** Administer the tests in the following order to every patient at each assessment visit.

#### **1. HOPKINS VERBAL LEARNING TEST - REVISED (HVLTR)**

This test has three parts and six alternate forms (only the first 4 forms will be used in this study):

**Part A - Free Recall:** Complete the three learning trials first

**Part B - Delayed Recall:** Complete after Trail Making Tests and COWAT

**Part C - Delayed Recognition:** Complete after Delayed Recall

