### 1.5 Neurocognitive Function Assessment

To assess our primary endpoint, we have chosen to use the Hopkins Verbal Learning Test (HVLT-R) test that has been used and validated in the phase III trial of motexafin gadolinium for patients with brain metastases. In this trial, compliance with NCF testing was 87% to 98% at baseline and 77% to 87% at 6 months (Meyers 2004). Our reasons for using this particular NCF test include: 1) its ease of use, 2) our institutional experience with its administration, and 3) its validation by RTOG for use in a prior multi-institution study. In RTOG 0018, a phase II trial to evaluate the feasibility of neurocognitive testing of brain metastasis patients receiving WBRT in the cooperative group setting, compliance was >90% prior to WBRT, >84% at the completion of WBRT, and >78% at one month after WBRT. Most non-compliance was attributed to patient-related factors such as decline in performance status (Regine 2004).

The version of the HVLT-R used in the phase III trial of motexafin gadolinium for patients with brain metastases, which for consistency and study comparability will be used in the present study, incorporates 6 different forms, helping to mitigate practice effects of repeated administrations. Each form includes 12 nouns (targets) with 4 words drawn from 3 semantic categories, which differ across the 6 forms. The test involves memorizing a list of 12 targets for 3 consecutive trials (immediate recall), identifying the 12 targets from a list of semantically related or unrelated items (immediate recognition), and recalling the 12 targets after a 20-minute delay (delayed recall). Raw scores are derived for total recall, delayed recall, retention (percentage retained), and a recognition discrimination index. Each patient will serve as his/her own control, as the difference in scores obtained at baseline and at pre-specified post-treatment intervals will be calculated.

Prior to initiation of treatment, all patients will undergo baseline NCF testing using a test battery consisting of the HVLT-R, Trail Making Test (TMT), Controlled Word Association Test (COWAT), and Mini-Mental Status Examination (MMSE). At that time, history regarding level of education reached will also be obtained. After

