#### 11.5 Administration of Neurocognitive, Fatigue, and Quality of Life Assessments

##### 11.5.1 Timing

11.5.1.1 Prior to initiation of treatment, all patients will undergo baseline neurocognitive, fatigue, and quality of life testing using this test battery. At that time, history regarding level of education reached will also be obtained. After completion of radiotherapy, all patients will undergo neurocognitive and fatigue evaluation at 3, 6, 9, 12, and 24 months after WBRT-HA/SIB.

11.5.1.2 Examiners will give patients a short break if the patient appears fatigued or otherwise in need of a few-minutes break.

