## **13.0 STATISTICAL CONSIDERATIONS**

### 13.1 Study Endpoints

#### 13.1.1 Primary Endpoint

Delayed recall, 3 months from the start of treatment as measured by the Hopkins Verbal Learning Test-Revised for delayed recall (HVLTR delayed recall)

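### Four HVLT-R forms are specified for six test sessions, so at least two sessions must reuse a word list, probably those at 12 and 24 months

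*Combined protocol and SAP*

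**What the plan says.** Section 1.5 describes the HVLT-R version to be used in this study as one that "incorporates 6 different forms, helping to mitigate practice effects of repeated administrations". Section 11.2.2.1 repeats the statement. Appendix III, in the HVLT-R test instructions, says the test has six forms but that "only the first 4 forms will be used in this study".

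Section 11.5.1 fixes the sessions. Before treatment, "all patients will undergo baseline neurocognitive, fatigue, and quality of life testing using this test battery", and afterwards "all patients will undergo neurocognitive and fatigue evaluation at 3, 6, 9, 12, and 24 months after WBRT-HA/SIB". Sections 1.5 and 12.0 give the same follow-up times. Appendix I also shows one session before treatment and five after it, although it labels the second follow-up column as 4 to 6 months.

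Item 7 of the general testing information in Appendix III says that the HVLT-R and COWAT "have alternate forms or versions in order to reduce the effects of practice". It adds: "The forms should continue to be alternated in this order for the duration of the study". It refers the examiner to the test instructions for the version to give at each session, but those instructions do not assign forms to visits. No section explains the limit of four or provides an adjustment for practice.

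**The concern.** The protocol treats re-exposure to a word list as a threat. It rotates lists, and it withholds copies of the tests so that patients cannot learn the material. Yet it takes up four of the six lists available for exactly six sessions. A patient who retains anything of a list heard before may score higher at the repeat, and decline from baseline would then look smaller. That is the direction of the trial's hypothesis (Section 13.2), and there is no concurrent control arm that would share the effect.

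The results exposed are secondary. Section 1.5 plans to compare each test at each follow-up time with baseline. Section 2.2.1 includes HVLT-R free recall, delayed recall and delayed recognition in time to neurocognitive failure. Section 13.3.2.1 uses change from baseline through 12 months.

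**Working it through.** **Inputs.** Sessions: 1 at baseline + 5 at follow-up = 6 (Section 11.5.1). Forms available: 6; forms used: 4 (Appendix III). Rotation: in a fixed order (Appendix III, general information, item 7). For patient numbers: 50 registered, 60% dead before 3 months, and 9 of 32 pilot patients with complete baseline and 3-month scores (all Section 13.2).

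**Minimum number of repeats.** Sessions minus distinct forms = 6 − 4 = 2. Enumerating all 4^6 assignments of four forms to six sessions confirms that none has fewer than two repeats. If the first four sessions use different forms, the repeats always fall at the fifth and sixth sessions. With six forms the minimum is 6 − 6 = 0.

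**Where the repeats fall under in-order rotation.** Session i receives form ((i − 1) mod 4) + 1:

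| Session | Four forms | Time since last use | Six forms |
|---|---|---|---|
| Baseline | 1 | – | 1 |
| 3 months | 2 | – | 2 |
| 6 months | 3 | – | 3 |
| 9 months | 4 | – | 4 |
| 12 months | 1 | 12 months | 5 |
| 24 months | 2 | 21 months | 6 |

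So 2 of the 5 follow-up sessions would reuse a list. At 12 months it is the baseline list, and at 24 months the 3-month list.

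**Primary endpoint.** Section 13.1.1 defines it as "Delayed recall, 3 months from the start of treatment". It compares form 1 with form 2, and neither has been heard before. The primary test and the sample size do not change.

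**Scale of a gain, if there is one.** Section 13.2 defines relative decline as (baseline score − follow-up score) / baseline score. A practice gain of g words at follow-up lowers this by g / baseline score. Delayed recall has 12 words, so each word gained removes at least 1/12 = 8.3 percentage points, and more when the baseline score is lower. The documents give no value for g at a gap of 12 or 21 months. It could be close to zero.

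**Patients alive at 12 months.** Only the 60% figure is in the plan; its continuation after 3 months is assumed.

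- 60% mortality in every 3-month period: 50 × 0.4^4 = 1.3.
- Hazard falling to a quarter after month 3: 50 × 0.4 × 0.4^(3/4) = 50 × 0.4 × 0.503 = 10.1.
- The same quarter hazard, starting from the pilot's share with complete 3-month data (9/32 = 28%): 50 × 0.281 × 0.503 = 7.1.

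The first two figures count patients alive. Patients tested would be fewer. Section 13.2 gives the target of 50; the Schema states 102, which would roughly double each figure.

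**The case against.** The strongest reply is that little depends on this. The primary comparison is untouched. Section 13.3.2.1 names 12 months only for Spearman correlations, and a similar upward shift in all patients would leave the ranks largely unchanged. Section 13.3 names no 24-month HVLT-R test. Time to neurocognitive failure has no stated threshold and no analysis in Section 13.3, and a failure scored at 3, 6 or 9 months cannot be hidden by a later repeat. All of this stands and limits the point to a minor one.

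Four stronger readings are tempting, and the documents do not support them:

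- *The late results are biased.* The documents show only that re-exposure is possible. They give no practice effect for a list last heard 12 or 21 months earlier.
- *The repeats are fixed at 12 and 24 months.* That follows from the rotation rule. No schedule is printed, and the forms packet is not part of the documents.
- *The test was chosen for its six forms.* Section 1.5 gives ease of use, institutional experience and earlier validation as its reasons. The six forms appear in the next paragraph as a helpful feature.
- *The correction is free of side effects.* Section 13.2 reports 32 patients already enrolled, and the documents do not say whether the six forms are equally difficult.

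It is also fair to say that HVLT-R is not the only test affected. COWAT has two alternate forms for the same six sessions, and no alternate form is described for the Trail Making Test. Six HVLT-R lists would not remove practice effects from the whole battery. They would remove a repeat that the protocol already has the means to avoid, on the test that carries the primary measure.

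**Conclusion.** The point holds as a minor one. Four forms for six sessions force at least two repeated lists, and this conflicts with Sections 1.5 and 11.2.2.1, which present six forms as mitigating practice effects. Placing the repeats at 12 and 24 months rests on in-order rotation. Any effect would make late decline look smaller in secondary HVLT-R change and in late failure events; its size is unknown and may be small. About 1 to 10 of 50 patients would be alive at 12 months, under the assumed death rates. A reader should not infer that the 3-month result or the sample size is in doubt: the primary endpoint is unaffected under the same rotation.

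**What to change.** In Appendix III, delete the four-form restriction and print a schedule that assigns forms 1, 2, 3, 4, 5 and 6 to baseline and to 3, 6, 9, 12 and 24 months. Reconcile this with Sections 1.5 and 11.2.2.1. Patients already enrolled move on to forms 5 and 6 where those visits are still due, which keeps their sequence so far intact. Flag in the data any late session done on a repeated list. If the sponsor prefers to keep four forms, the protocol should give the reason, print the schedule, and amend the two sections.

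The cost is two more existing forms in the packet and, among patients already enrolled, possibly a mix of repeated and new lists at the late visits. The gain is also modest. Of the 18 patients still to be recruited under Section 13.2, the two assumed death rates leave 18 × 0.4^4 = 0.5 to 18 × 0.4 × 0.503 = 3.6 alive at 12 months.
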